5.2 Exclusion Criteria

Participants are excluded from the study if any of the following criteria apply:

[Part A/Part C]

Medical Conditions

- 1 Estimated glomerular filtration rate (eGFR) < 60 mL/min/1.73m² using the Japanese equation. (eGFR = 194 × sCr (mg/dL)^{-1.094} × Age^{-0.287} × α, where α is 1 for males and 0.739 for females)
- 2 History or presence of gastrointestinal, hepatic, or renal disease or any other conditions known to interfere with absorption, distribution, metabolism, or excretion of drugs.
- 3 Any uncontrolled or serious disease, or any medical (e.g., known major active infection or major haematological, renal, metabolic, gastrointestinal, or endocrine dysfunction) or surgical condition that, in the opinion of the Investigator, may either interfere with participation in the clinical study and/or put the participant at significant risk.
- 4 Blood dyscrasias with increased risk of bleeding including idiopathic thrombocytopenic purpura and thrombotic thrombocytopenic purpura or symptoms of increased risk of bleeding (frequent bleeding gums or nose bleeds). Or participants receiving anti-coagulation therapy.
- 5 History of major bleed or high-risk of bleeding diathesis.
- 6 Subjects with a high 10-year risk of coronary heart disease as calculated using the Suits score (Participants classified in high risk class).
- 7 Malignancy (except non-melanoma skin cancers, cervical in-situ carcinoma, breast ductal carcinoma in-situ, or Stage 1 prostate carcinoma) within the last 10 years.
- 8 Recipient of any major organ transplant, e.g., lung, liver, heart, bone marrow, kidney.

- 9 LDL or plasma apheresis within 12 months prior to randomization.
- 10 Heart rate after 10 minutes of sitting rest < 50 or > 100 beats per minute (bpm).
- 11 Uncontrolled hypertension defined as sitting SBP > 140 mmHg or DBP > 90 mmHg.
- 12 Any laboratory values with the following deviations at the Screening Visit; test may be repeated at the discretion of the Investigator if abnormal:
 - Any positive result on screening for hepatitis B, hepatitis C, or human immunodeficiency virus (HIV).
 - Alanine aminotransferase/transaminase (ALT) > 1.5 × upper limit of normal (ULN).
 - Aspartate aminotransferase/transaminase (AST) > 1.5 × ULN.
 - Creatinine > 1.5 mg/dL.
 - White blood cell (WBC) < lower limit of normal (LLN).
 - Hemoglobin < 12 g/dL in men or < 11 g/dL in women
 - Platelet count ≤ LLN.
 - Activated partial thromboplastin time (aPTT) > ULN and PT > ULN.
 - Urinary albumin creatinine ratio (UACR) > 11 mg/mmol (100 mg/g).
- 13 Any clinically important abnormalities in rhythm, conduction, or morphology of the resting ECG and any clinically important abnormalities in the 12-lead ECG as judged by the Investigator that may interfere with the interpretation of QTc interval (Corrected QT Interval by Fridericia [QTcF] > 450 ms) changes, including abnormal ST-T-wave morphology, left ventricular hypertrophy, test may be repeated at the discretion of the Investigator if abnormal.
- 14 Known or suspected history of drug abuse as judged by the Investigator.
- 15 Smokers with > 10 cigarettes/day and unable to comply with the nicotine restriction during the study.
- 16 History of alcohol abuse or excessive intake of alcohol as judged by the Investigator.
- 17 Excessive intake of caffeine-containing drinks or food (e.g., coffee, tea, chocolate,) as judged by the Investigator.
- 18 Use of drugs with cytochrome P450 enzyme inducing properties such as St John's Wort within 3 weeks before the first administration of IMP.
- 19 Antiplatelet therapy, other than low-dose aspirin ≤ 100 mg/day, within 1 month prior to randomization.
- 20 Mipomersen (not approved in Japan), or lomitapide within 12 months prior to randomization.
- 21 Previous administration of AZD8233 or other PCSK9 inhibition treatment (approved or IMP).

- 22 Use of any herbal remedies, megadose vitamins (intake of 20 to 600 times the recommended daily dose) and minerals during the 2 weeks prior to the first administration of IMP or 5 half-lives, whichever is longer.
- 23 History of severe allergy/hypersensitivity or ongoing clinically important allergy/hypersensitivity, as judged by the Investigator or history of hypersensitivity to drugs with a similar chemical structure or galactosamine-conjugated antisense oligonucleotides.
- 24 Any clinically important illness, medical/surgical procedure or trauma within 4 weeks of the first administration of IMP. History or evidence of any other clinically significant disorder (e.g., cognitive impairment), condition or disease other than those outlined above that, in the opinion of the Investigator or AstraZeneca physician, if consulted, may compromise the ability of the subject to give written informed consent, would pose a risk to subject safety, or interfere with the study evaluation, procedures, or completion.

Prior/concurrent clinical study experience

- 25 Participation in another clinical study with an investigational product administered in the last 3 months prior to randomisation or 5 half-lives from last dose to first administration of study intervention, whichever is the longest.
- 26 Received another new chemical entity (defined as a compound which has not been approved for marketing) within 30 days of last follow-up to first administration of the IMP of this study or 5 half-lives from last dose to first administration of IMP, whichever is the longest.
- 27 Use of other IMP or devices during the course of the study.

Other exclusions

- 28 Involvement in the planning and/or conduct of the study (applies to both AstraZeneca staff and/or staff at the study site or their close relatives).
- 29 Judgment by the Investigator that the patient should not participate in the study if the participant is unlikely to comply with study procedures, restrictions and requirements.
- 30 Previous enrolment or randomisation into the present study.
- 31 Participants who cannot communicate reliably with the Investigator.
- 32 Vulnerable participants, e.g., kept in detention, protected adults under guardianship, trusteeship, or committed to an institution by governmental or juridical order.
- 33 Plasma donation within 1 month of the Screening Visit. For male participants, donation of whole blood or significant blood loss in excess of 400 mL within 3 months prior to screening visit and for female participants, donation of whole blood or significant blood loss in excess 400 mL within 4 months prior to screening visit.

References for eGFR and SBP threshold, and [The Suita score](#) (J Atheroscler Thromb, 2018):

- eGFR - based on the mildly-decreased levels proposed by the Japanese Society of Nephrology.
- SBP - based on the hypertension criterion proposed by the Japanese Society of Hypertension.

[Part B]

Medical conditions

- 1 eGFR < 40 mL/min/1.73m² using the Japanese equation at Visit 1. ($eGFR = 194 \times sCr (mg/dL)^{-1.094} \times Age^{-0.287} \times \alpha$, where α is 1 for males and 0.739 for females)
- 2 History or presence of gastrointestinal, hepatic, or renal disease or any other conditions known to interfere with absorption, distribution, metabolism, or excretion of drugs.
- 3 Any uncontrolled or serious disease, or any medical (e.g., known major active infection or major haematological, renal, metabolic, gastrointestinal, or endocrine dysfunction) or surgical condition that, in the opinion of the Investigator, may either interfere with participation in the clinical study and/or put the participant at significant risk.
- 4 Poorly controlled type 2 diabetes mellitus (T2DM), defined as Haemoglobin A1c (HbA1c) > 10% at Visit 1.
- 5 Acute ischaemic cardiovascular event in the last 12 months prior to randomization.
- 6 Heart failure with New York Heart Association (NYHA) Class III-IV.
- 7 Blood dyscrasias with increased risk of bleeding including idiopathic thrombocytopenic purpura and thrombotic thrombocytopenic purpura or symptoms of increased risk of bleeding (frequent bleeding gums or nose bleeds). Or participants receiving anti-coagulation therapy.
- 8 High-risk of bleeding diathesis as judged by the Investigator.
- 9 Malignancy (except non-melanoma skin cancers, cervical in-situ carcinoma, breast ductal carcinoma in-situ, or Stage 1 prostate carcinoma) within the last 10 years.
- 10 Recipient of any major organ transplant, e.g., lung, liver, heart, bone marrow, renal.
- 11 LDL or plasma apheresis within 12 months prior to randomization.
- 12 Uncontrolled hypertension defined as average supine SBP > 160 mmHg or DBP > 90 mmHg at Visit 1 or Visit 3.
- 13 Heart rate after 10 minutes supine rest < 50 bpm or > 100 bpm at Visit 1 or Visit 3.
- 14 Any laboratory values with the following deviations at the Screening Visit; test may be repeated at the discretion of the Investigator if abnormal:
 - Any positive result on screening for hepatitis B, hepatitis C, or HIV
 - ALT > 1.5 × ULN
 - AST > 1.5 × ULN

- Total bilirubin (TBL) > ULN
- Alkaline phosphatase (ALP) > 1.5 × ULN
- WBC < LLN
- Hemoglobin < 12 g/dL in men or < 11 g/dL in women
- Platelet count ≤ LLN
- aPTT > ULN and PT > ULN
- UACR > 11.3 mg/mmol (100 mg/g)
- Urine protein/creatinine (UPCR) > 300 mg/g

15 Any clinically important abnormalities in rhythm, conduction, or morphology of the resting ECG and any clinically important abnormalities in the 12-lead ECG as judged by the Investigator.

16 QTcF > 470 ms; high degree atrioventricular (AV)-block grade II-III and sinus node dysfunction with significant sinus pause untreated with pacemaker; and cardiac tachyarrhythmias.

17 Known or suspected history of drug abuse as judged by the Investigator.

18 History of alcohol abuse or excessive intake of alcohol as judged by the Investigator.

19 Mipomersen (not approved in Japan), or lomitapide within 12 months prior to randomization.

20 Previous administration of AZD8233 or other PCSK9 inhibition treatment (approved or IMP).

21 History of severe allergy/hypersensitivity or ongoing clinically important allergy/hypersensitivity, as judged by the Investigator or history of hypersensitivity to drugs with a similar chemical structure or galactosamine-conjugated antisense oligonucleotides.

22 Any clinically important illness, medical/surgical procedure or trauma within 4 weeks of the first administration of IP. History or evidence of any other clinically significant disorder (e.g., cognitive impairment), condition or disease other than those outlined above that, in the opinion of the Investigator or AstraZeneca physician, if consulted, may compromise the ability of the subject to give written informed consent, would pose a risk to subject safety, or interfere with the study evaluation, procedures, or completion.

Prior/Concurrent Clinical Study Experience

23 Participation in another clinical study with an investigational product administered in the last 3 months prior to randomisation or 5 half-lives from last dose to first administration of study intervention, whichever is the longest.

24 Received another new chemical entity (defined as a compound which has not been approved for marketing) within 30 days of last follow-up to first administration of the

IMP of this study or 5 half-lives from last dose to first administration of IMP, whichever is the longest.

25 Use of other IMP or devices during the course of the study.

Other Exclusions

26 Involvement in the planning and/or conduct of the study (applies to both AstraZeneca staff and/or staff at the study site or their close relatives).

27 Judgment by the Investigator that the patient should not participate in the study if the patient is unlikely to comply with study procedures, restrictions and requirements.

28 As judged by the Investigator, any evidence of disease conditions that, in the Investigator's opinion, make it undesirable for the participant to participate in the trial.

29 Previous enrolment or randomisation in the present study.

30 Participants who cannot communicate reliably with the Investigator.

31 Vulnerable participants, e.g., kept in detention, protected adults under guardianship, trusteeship, or committed to an institution by governmental or juridical order.

32 Plasma donation within 1 month of the screening visit. For male participants, donation of whole blood or significant blood loss in excess of 400 mL within 3 months prior to screening visit. For female participants, donation of whole blood or significant blood loss in excess of 400 mL within 4 months prior to screening visit.

Optional Genetic Sampling

[Part A/Part C]

Not applicable

[Part B]

Exclusion from this genetic research may be for any of the exclusion criteria specified for the main study or any of the following:

33 Previous allogeneic bone marrow transplant.

34 Non-leukocyte depleted whole blood transfusion within 120 days of genetic sample collection.

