1.3 Schedule of Activities

[Part A]

Randomization should only proceed if all required assessments have been performed and all inclusion/exclusion criteria as well as other protocol restrictions have been evaluated; see Sections 5 and 6.5.

Dosing should only be carried out for participants if all required assessments have been performed and evaluated. Dosing is not allowed to proceed until the Investigator has determined that the results are within acceptable range according to the defined stopping criteria. Laboratory assessment results should also be reviewed at every visit to ensure that stopping criteria have not been met.

Assessments scheduled to be done at the same time may be initiated based on the sequence below:

- 1 ECGs
- 2 Vital signs (Systolic Blood Pressure [SBP] and Diastolic Blood Pressure [DBP]), pulse rate, and temperature, if appropriate
- 3 Blood sampling
- 4 Dose administration

Pre-dose assessments may be performed within 30 minutes prior to dosing.

Table 1 Schedule of Activities (Part A)

Visit Number	Screening	Treatment Period					Follow-up Period			Corre-sponding Section in Protocol	
		1	2	3, 6	4, 5, 7, 8	9	Telephone contact ^k	10 to 16	17 (Final Follow-up Visit/ ED Visit)		
Study Day/Week	Days -28 to -4	Day -1	Days 1 to 3	Days 8 ^a , 29	Days 15, 22, 36, 44	Day 56	Days 57 to 59	Day 64	Weeks 2, 4, 6, 8, 10, 12, 14 (after last dose)	Week 16 (after last dose)	
Visit Window	-	-	-	± 1 day	± 1 day		± 1 day	+2 days	± 2 days	± 2 days	
Informed consent	X										Appendix A 3
Inclusion/exclusion criteria ^b	X	X									Sections 5.1, 5.2
Demographic data	X										Section 9.4.1
Weight and height (BMI) ^c	X	X					X (Day 57)			X	Section 8.2.1
Medical history	X										Section 8
Concomitant medication	X	X	X	X	X	X	X	X	X		Section 6.5
Drug abuse and alcohol screen ^d	X					X					Section 5.3.2, 5.2
Smoking history	X										Section 5.3.2

Table 1 Schedule of Activities (Part A)

Visit Number	Screening	Treatment Period					Follow-up Period			Corre-sponding Section in Protocol	
	1	2	3, 6	4, 5, 7, 8	9	Telephone contact ^k	10 to 16	17 (Final Follow-up Visit/ ED Visit)			
Study Day/Week	Days -28 to -4	Day -1	Days 1 to 3	Days 8 ^a , 29	Days 15, 22, 36, 44	Day 56	Days 57 to 59	Day 64	Weeks 2, 4, 6, 8, 10, 12, 14 (after last dose)	Week 16 (after last dose)	
Visit Window	-	-	-	± 1 day	± 1 day	± 1 day		+2 days	± 2 days	± 2 days	
Viral serology ^e	X										Section 8.2.5
Pregnancy test (females only)	X ^o		X ^p								Section 8.2.4

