
Cardiovascular Criteria

- Two or more participants who receive AZD8233, have QT (ECG interval measured from the onset of the QRS complex to the end of the T wave) interval corrected (QTc) prolongation, defined as the QT interval corrected for heart rate using Fridericia's formula (QTcF) > 500 ms, or a prolongation from baseline of > 60 ms, confirmed (persistent for at least 5 min) and determined post-dose either during continuous 12-lead ECG monitoring or on a repeat 12-lead ECG.
- Two or more participants who receive AZD8233, have tachycardia defined as resting supine heart rate > 125 bpm persisting for at least 10 minutes.
- Two or more participants who receive AZD8233, have symptomatic bradycardia defined as resting supine heart rate < 45 bpm or asymptomatic bradycardia defined as resting supine heart rate < 30 bpm while awake persisting for at least 10 minutes.
- Two or more participants who receive AZD8233, develop hypertension, defined as an increase by > 40 mmHg from baseline or in resting supine SBP above 180 mmHg and persisting for at least 10 minutes.
- Two or more participants who receive AZD8233 develop hypotension, defined as an asymptomatic decrease of > 20 mmHg for SBP to below 70 mmHg persisting at least 10 minutes, or a symptomatic SBP decrease of > 20 mmHg (excluding vasovagal reaction).

Laboratory Findings

- One or more participants who receive AZD8233 fulfill Hy's Law (HL) defined as an increase in AST or ALT $\geq 3 \times$ ULN and TBL $\geq 2 \times$ ULN, where no other reason can be found to explain the combination of increases, e.g., elevated serum ALP indicating cholestasis, viral hepatitis, or another drug. The elevations do not have to be at the same time or within a specified time frame (see [Appendix E](#) for follow-up procedures).
- Two or more participants who receive AZD8233 have confirmed $> 3 \times$ ULN of either ALT or AST or $> 2 \times$ ULN for TBL or ALP.
- Two or more participants who receive AZD8233 have confirmed leukocyte count $< 2.0 \times 10^9/L$.
- Two or more participants who receive AZD8233 have confirmed neutrophil count $< 1.0 \times 10^9/L$.
- Two or more participants who receive AZD8233 have confirmed platelet count $< 75 \times 10^9/L$.
- Two or more participants who receive AZD8233 have a platelet count reduction of 50% or more from baseline.
- Two or more participants treated with AZD8233 have confirmed increase in serum creatinine (SCr) > 0.3 mg/dL (26.5 μ mol/L) from baseline.

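### Parts A and C set no entry limit for bilirubin or ALP, so a participant can pass every numeric criterion while already above a stopping threshold (low priority)

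*Protocol*

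**What the plan says.** **Entry, Parts A and C.** Protocol Section 5.2, criterion 12, opens with "Any laboratory values with the following deviations at the Screening Visit; test may be repeated at the discretion of the Investigator if abnormal". It then lists viral serology, ALT ("Alanine aminotransferase/transaminase (ALT) > 1.5 × upper limit of normal (ULN"), AST ("Aspartate aminotransferase/transaminase (AST) > 1.5 × ULN"), creatinine, white cells, haemoglobin, platelets, aPTT with PT, and UACR. TBL and ALP are not in the list. Both are in the Part A/C chemistry panel in Section 8.2.4, and Tables 1 and 3 schedule chemistry at screening and on Day -1.

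**Entry, Part B.** Criterion 14 of the Part B list excludes "Total bilirubin (TBL) > ULN" and "Alkaline phosphatase (ALP) > 1.5 × ULN".

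**Stopping rules, Parts A and C.** Under the Laboratory Findings heading, Section 7.1 counts two or more AZD8233 recipients with a confirmed value above 3 × "ULN of either ALT or AST or $> 2 \times$ ULN for TBL or ALP". This item has no baseline term. Elsewhere in the same list, two or more participants count if they "have a platelet count reduction of 50% or more from baseline", and the serum creatinine items are also relative to baseline.

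**Pre-dose check.** Section 1.3 states for Part A, and repeats for Part C: "Dosing is not allowed to proceed until the Investigator has determined that the results are within acceptable range according to the defined stopping criteria".

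**The concern.** An entry list and a stopping list should fit together: whoever is admitted should start on the safe side of every stopping threshold, or the threshold should be defined as a change. For ALT and AST the protocol leaves that room. For TBL and ALP in Parts A and C it does neither. A long-standing, stable elevation above 2 × ULN passes criterion 12 and is already over the line in Section 7.1.

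Each part has only 8 participants on active drug, and safety is the primary objective. One of the two laboratory cases could then be supplied by a value that was there before the first dose. The alternative is a randomised participant who cannot be dosed, in a part with about 11 places. Section 5.2 gives no reason why the Phase 1 parts omit two limits that Part B includes.

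**Working it through.** Parts A and C have no formal sample-size calculation and the plan states no figure on this point, so there is nothing to reproduce. The check is a comparison of texts.

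**Step 1. Entry limit against stopping threshold (multiples of ULN; Sections 5.2 and 7.1).**

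| Analyte | A/C entry | A/C stop | Stop ÷ entry | B entry | B stop | Stop ÷ entry |
|---|---|---|---|---|---|---|
| ALT, AST | 1.5 | 3 | 3/1.5 = 2.0 | 1.5 | 3 | 2.0 |
| TBL | none | 2 | undefined | 1 | 2 | 2/1 = 2.0 |
| ALP | none | 2 | undefined | 1.5 | 2 | 2/1.5 = 1.33 |

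Every row has room between entry and stopping except TBL and ALP in Parts A and C. The Part B stopping item also lacks a baseline term, but its entry limits make one unnecessary.

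**Step 2. Follow one participant.** Suppose TBL is 2.5 × ULN at screening and stays there.

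- Criterion 12: not breached.
- Criteria 2, 3 and 24: these concern hepatic disease and conditions affecting drug disposition, serious disease, and other disorders in the investigator's opinion. None gives a TBL or ALP value, so exclusion depends on judgement.
- Pre-dose check: read against the thresholds in Section 7.1, the value is not acceptable and dosing stops. The participant is eligible under 5.2 but cannot be dosed under 1.3.
- If the investigator nevertheless accepts the value and doses: once confirmed, it meets the Laboratory Findings item, although nothing has changed on treatment.

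The two outcomes are alternatives. Only a dosed participant counts in Section 7.1.

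**Step 3. Scale, as illustration only.** Let π be the prevalence of baseline TBL or ALP above 2 × ULN among those enrolled. The documents do not give π, so the values below are assumptions. They also assume that nobody is removed by judgement or by the pre-dose check. With 8 active participants:

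- P(at least 1) = 1 − (1 − π)^8
- P(at least 2) = 1 − (1 − π)^8 − 8π(1 − π)^7

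| π | P(at least 1) | P(at least 2) |
|---|---|---|
| 0.5% | 3.9% | 0.07% |
| 1% | 7.7% | 0.27% |
| 2% | 14.9% | 1.0% |
| 5% | 33.7% | 5.7% |

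At low prevalence, pre-existing elevations alone would almost never supply both cases.

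To combine them with on-treatment cases, let q be the per-participant rate of an on-treatment case and p = 1 − (1 − q)(1 − π). Section 2.2 reports 6 ALT rises of 3 to below 6 × ULN among more than 120 exposed, so q is at most about 6/120 = 5%. With q = 5% and π = 0, P(at least 2 of 8) is 5.7%. With π = 0.5%, p = 1 − 0.95 × 0.995 = 0.05475 and the probability is 6.7%. With π = 1%, p = 0.0595 and it is 7.8%. With q = 2%, the same three values are 1.0%, 1.6% and 2.2%.

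**The case against.** The strongest reply is that the protocol already handles this, and that the consequences are easily overstated. Much of that stands.

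- **Automatic hold.** A reader might infer that two TBL or ALP cases stop the study. The temporary-hold sentence in Section 7.1 sits under General Criteria and introduces only related SAEs and related severe AEs; the synopsis hold list contains the same two. The laboratory list feeds individual stopping and, in Part A, a review of the totality of data after which the SRC may decide not to proceed. A known benign elevation could be discounted there.
- **Gating Phase 3 through Part C.** Amendment 4 removed the SRC from Part C, and Section 7.1 ties the rules to decisions after Parts A and B only. The documents give no such gate.
- **A one-participant route through Hy's Law.** This also needs a transaminase value of at least 3 × ULN, the Section 7.1 item excludes cases with another explanation, and Appendix E asks whether the criteria were met before treatment. A raised TBL alone does not produce it.
- **Misleading tables.** The Part A and Part C SAPs (Section 4.2.3.4) summarise maximum post-baseline TBL. They also give change from baseline, shift tables for selected parameters and individual bilirubin plots, so a stable elevation would be visible as one.
- **A large jump in probability.** If one such participant is already dosed and q = 5%, the chance of a second case among the other 7 is 1 − 0.95^7 = 30%, against 5.7% otherwise. The arithmetic is right, but it assumes the participant is present and dosed.
- **A baseline reference exists.** Section 7.1 stops individual dosing on a significant change in the listed parameters, which could be read as relative to baseline. The TBL and ALP item does not say so, while its neighbours do.
- **Judgement and the pre-dose check suffice.** They would probably catch most such people. Section 1.3 also requires other protocol restrictions to be evaluated before randomisation, but it points to Sections 5 and 6.5, not to the stopping list. If the pre-dose check is what catches the person, the eligibility list admitted someone who could not be dosed.

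**Conclusion.** The mismatch is real and limited. In Parts A and C a participant with TBL or ALP already above 2 × ULN breaches no numeric entry criterion. That participant is then either undosable under the pre-dose check or, if dosed, countable as one of two laboratory cases without any on-treatment change. This follows from the text and needs no assumption about rates.

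Its size does rest on assumptions. The prevalence is not in the documents, the 5% on-treatment rate is an upper bound from ALT rises seen without any bilirubin increase, and some people would be excluded by judgement. The probabilities above are illustration, not estimates. The documents do not support the reading that a baseline elevation would halt the study or, by itself, block later development. This is a low-priority consistency point. It cannot change Part A, whose SAP amendment history records post-lock changes from May 2022.

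**What to change.** Reconcile criterion 12 of the Part A/C exclusions with the stopping rules in Section 7.1 and the pre-dose check in Section 1.3, so that nobody can be eligible while already meeting a TBL or ALP stopping criterion. There are two routes: an entry limit for both analytes, for which Part B already has wording, or a baseline reference in the stopping item, as the platelet-reduction and creatinine items have. The sponsor should choose the route and the values on clinical grounds.

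The cost is a short amendment. No new test is needed, because both analytes are already measured at screening. An entry limit would add a few screen failures, softened by the repeat-test allowance already in criterion 12. The change could help only Part C, if it is still enrolling, and any later protocol that reuses these lists.
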